INVESTIGATOR STUDY PLAN – REQUIRED

**ID:
H00011523**

**Speech, Linguistic and Acoustic Markers in
Parkinson's Disease**

NCT04273672

INVESTIGATOR STUDY PLAN – REQUIRED

1) Title

Speech, language and acoustic markers in Parkinson disease (SLAM-PD)

2) IRB Review History*

NA, this is the initial application.

3) Objectives*

- 1) To develop markers of cognitive function in Parkinson's disease (PD) that can be assessed through speech and language

We hypothesize that speech and language tasks will yield biomarkers that can serve as proxies for performance on standard cognitive measures

- 2) To assess the feasibility of implementing technology such as smartphone applications and tablet-based tasks to aid in the monitoring of vocal biomarkers in PD

We hypothesize PD patients will be amenable and able to perform mobile app collection of vocal biomarker data.

- 3) To evaluate the impact of motor, cognitive, and affective symptoms and therapy on vocal biomarkers.

We hypothesize that vocal biomarkers of disease burden will fluctuate based on therapeutic response and will correlate to severity of motor, cognitive, and affective symptoms.

4) Background*

Speech impairment occurs in almost 90% of individuals with Parkinson disease (PD)¹. PD patients have characteristic changes in speech, including changes in the coordination, changes in frequency and amplitude, changes in rhythm and rate, and changes in vocal quality, including breathiness, harshness, and hypernasality². Changes in PD speech are thought to be caused by the neurodegenerative process of PD, specifically the impact on dopaminergic neurons in the substantia nigra and the subsequent dysfunction in the basal ganglia, a brain circuit involved in motor and cognitive control. While general speech impairment in PD has been characterized relative to healthy individuals, it is unknown if certain speech characteristics reflect particular motor or cognitive symptoms. Additionally, speech impairment may vary within an individual in response to medications and other therapies.

Changes in speech may also be sensitive to subtle, early symptoms in PD such as cognitive dysfunction. While it is known that cognitive changes frequently occur early in the course of PD, these subtle deficits may be difficult to detect clinically. For instance,

INVESTIGATOR STUDY PLAN – REQUIRED

PD patients may report word finding difficulty (WFD) during spontaneous speech before objective cognitive deficits develop. Spontaneous speech may be a powerful tool to assess a range of cognitive functions because it requires multiple simultaneous cognitive processes (e.g. lexical retrieval, grammatical and syntactical structuring, organization of narrative) occurring in real-time to attain fluency and accuracy.

Previous work in this area has focused on the relationship between vocal biomarkers and motor symptoms. Authors have successfully predicted PD motor severity based on several vocal features^{3,4}. An observational study has recently identified a link between clinician-rated speech symptoms and cognitive decline⁵. However, rating scales do not capture the data-rich acoustic and linguistic characteristics of speech. To our knowledge, there are no published reports using quantitative, objective speech parameters to monitor cognitive function in PD. In preliminary work, we have identified a potential relationship between WFD and pausing in speech that may depend on the location of the pause within the sentence structure⁶. We have also identified a cluster of acoustic and phoneme-related parameters that correlate significantly with global cognition independently of motor severity⁷. We therefore hypothesize that by combining quantitative speech and language assessment, we will be able to develop valid, sensitive tools to detect, monitor and predict cognitive changes in PD. Since PD symptoms vary both within and between days, and in response to medications, we will also use smartphone and tablet technology to obtain quick, remote and frequent speech data. By capitalizing on the ability to easily monitor speech remotely, we will develop assessment tools that can be implemented broadly.

We propose to enroll PD patients with (n=50) and without (n=50) MCI and controls (n=50). We will compare speech acoustic and linguistic measures in tasks that evaluate speech production and comprehension. We will combine measures into models to discriminate by disease and cognitive status. Acoustic data will also be automated and assessed using machine-learning methods to enable future large scale data analysis.

5) Inclusion and Exclusion Criteria*

This study will include adult patients >18 years of age with no upper age limit with PD (diagnosed by a Movement Disorders specialist according to standard clinical diagnostic methods) and healthy controls (HC) who do not have PD or other neurological disorders.

Patients and controls with dementia based on screening assessment (Montreal Cognitive Assessment, MoCA, score < 21) will be excluded.

Patients without smartphone access will be excluded from the smartphone sub-study.

INVESTIGATOR STUDY PLAN – REQUIRED

The following special populations will not be included: Adults unable to consent, individuals who are not yet adults (i.e., younger than 18 years: infants, children, teenagers), pregnant women, and prisoners.

Non-English speaking individuals will be excluded from this study since our linguistics outcomes of interest are based on norms and preliminary data from English speakers, and are specific to the grammatical and syntactic structure of the English language.

People with visual impairment may be excluded because the speech and cognitive tasks are reaction timed measures and it would not be scientifically useful to include any subjects that require extra time for reading due to their vision or required use of braille. There are no standard norms available for these measures to correct for vision impairment, and the sample size will not be large enough for the study team to create those norms. However, reasonable accommodations will otherwise be made to include individuals with some degree of visual impairment.

Table 5.1 Inclusion and Exclusion Criteria

Group	Inclusion Criteria	Exclusion Criteria
PD	Diagnosis of PD (UK PD Brain Bank Criteria) ⁸	Any neurological disorder other than PD
	Disease duration \geq 2 years ⁹	Deep brain stimulator placement
		Severe, unstable psychiatric disorder
		Unintelligible speech due to effects of PD
PD and controls	MCI or normal cognition (MDS Task Force Level II criteria) ¹⁰	Diagnosis of dementia (DSM-5)
	Age of PD onset >35 yrs or age >35 yrs (control)	Non-English primary language speaker
		Visual acuity or color vision impairment that would interfere with cognitive testing
		Other voice, speech or swallowing disorders or history of surgery involving palate/hasopharynx/larynx/vocal cords
Controls		Current or past history of any neurological disorder

6) Study-Wide Number of Subjects*

N/A

7) Study-Wide Recruitment Methods*

N/A This is not a multicenter

study.

8) Study Timelines*

Planned enrollment duration- 24 months

Planned duration of study for each participant- main study: 1 screening session and 1 study visit less than 3 months apart; smartphone app sub-study: 4 weeks following the study visit

INVESTIGATOR STUDY PLAN – REQUIRED

Planned duration of the study- approximately 48 months. Approximately 24 months to enroll and approximately 24 months for complex data analysis and development of analytical software and computerized algorithms.

The goal is to begin actively enrolling into this study once IRB approval is received or November 2019 whichever comes first. Enrollment is estimated to be achieved by the fall of 2021. Data analysis is estimated to be completed by the fall of 2023.

9) Study Endpoints*

The primary outcomes will be 1) development of a model using speech acoustic markers to classify PD participants by cognitive status, 2) identification of linguistic markers (pausing, syntax) associated with cognitive status, and 3) identification of changes in speed and accuracy of syntax comprehension that correlate with cognitive status.

10) Procedures Involved*

Potential participants will undergo a preliminary screening session. Interested participants will be asked if they have Parkinson disease, their year of clinical diagnosis, and if they have deep brain stimulation for any indication. PD and control participant will be asked questions about neurological and psychiatric disorders and disorders or procedures that may have affected their voice (see screening questionnaire). Both groups will be asked if they have a smartphone that is compatible with the Speech Vitals app (Aural Analytics, iOS running 12.4 or later, Andriod devices running 6.0 or later).

If the potential participant meets all criteria, t, they will undergo a screening global cognitive assessment (Montreal Cognitive Assessment, MoCA). They will be excluded if MoCA <21. They will also be excluded if they have severe visual impairment such that they cannot comfortably read the text of the MoCA. , Screening sessions will occur in the offices of study personnel at UMass Memorial Medical Center or remotely via videoconference and will take approximately 30 minutes total. This video will not be stored. If time and space allow, this visit may be conducted on the same day as a participant's regularly scheduled Neurology clinic visit, either before or after the physician visit. The participant's name, phone number, appointment date/time, and yes/no if they were eligible will be recorded in a screening log. When enrollment is complete, the screening call log will be disposed of in a UMass Memorial Medical Center HIPAA-compliant bin. Any collected data from participants who were ineligible or chose not to participate will thereby be destroyed.

INVESTIGATOR STUDY PLAN – REQUIRED

All participants who remain eligible will be educated about the study and undergo the informed consent procedure. Both the MoCA and HIPAA authorization are paper forms. If the participant is unable to come to UMass to complete these forms, they can be mailed or emailed to the participant prior to the initial visit and discussed in detail over videoconference to simulate the experience that would occur in the clinic setting. Any uncertainties regarding participant eligibility will be discussed directly with the study PI before any further study activities occur.

The team plans to provide study documents such as the consent form and prompts for speech protocol in large font print for those with visual impairments. Similarly, the language comprehension task on the laptop will be programmed with the largest font that is practical.

Once a participant has signed the informed consent and HIPAA authorization, the following data will be collected by a member of the study team:

- Basic demographic information: sex, age, years of education, duration of PD if applicable, list of medical conditions medication list (PD and controls, all medications) (<5 min)
- Rating scale for symptom assessment and motor examination will be performed and rated by an experienced clinician on the study team (Movement Disorders Society Unified Parkinson Disease Rating Scale, MDS-UPDRS¹¹) (<10 min)
- Timed up and go (TUG)¹², a timed mobility assessment of gait (<15 min)
 - For the TUG, participants will wear 4 wireless, Opal inertial sensors (APDM, Inc. sampling at 128Hz) mounted on the sternum, waist, and on each foot, to quantify gait and joint kinematics.
 - The participants will perform the TUG once and the total time will be recorded. The participants will then perform the TUG while performing a dual-task of simultaneously listing words that begin with the letter “S” and the total time will be recorded.
- Core cognitive/neuropsychological assessments (approx. 60 min)- MoCA¹³, Trail-making test A & B, Symbol digit modalities test, Clock copy, Boston Naming Test (30 item odd), Animal naming, Letter-guided verbal fluency, Judgement of Line Orientation (15 item odd), Boston Diagnostic Aphasia Examination¹⁴ (BDAE; verb naming

INVESTIGATOR STUDY PLAN – REQUIRED

and fluency, embedded sentences), digit span (WAIS-R), Hopkins verbal learning test – R immediate, letter number sequencing, HVLT-R Delay and Recognition, brief visual memory test-R), BVMT-R Delayed and Recognition. Other tests may be added if time permits- logical memory I (WMS-R, Anna Thompson story, logical memory II, Stroop (golden version), Shipley-2 vocab subtest) Participants will be recorded while performing certain oral portions of the above measures.

- Penn Daily Activities Questionnaire for Parkinson's Disease¹⁷ (PDAQ) (5 min)
- Geriatric depression scale¹⁸ (GDS) (1-2 min)
- Parkinson's Anxiety Scale¹⁹ (1-2 min)
- Clinical Dementia Rating (CDR) worksheet: The participants will complete the subject section of the questionnaire during the study visit, and an informant or caregiver will also be contacted by phone after the study visit or in person if present at the study visit to complete the informant section of the questionnaire. During the visit, the CDR should only take 5 minutes with the participant. The CDR administered during the follow-up phone call to the informant or caregiver should take between 10 and 15 minutes.
- Speech and language production measures: participants will be recorded while performing a variety of standard speech and language tests (including but not limited to sustained phonation of vowel sounds, reading nonsense words, reading sentences and passages, description of a picture of a scene, sentences that include a Stroop color-word task)
- After the study visit, please note that the study team may re-contact participants via phone if further color discrimination testing is deemed necessary based on subject results. The rationale for further color discrimination testing is based on prior research showing that Parkinson's disease contributes to some degree of color discrimination deficit. If participants agree to do the color discrimination testing, they will take a D15 Color Hue Test and a traditional Stroop Test via Zoom. Each assessment should take no more than 5 minutes to complete.
- Participants will be asked to perform manual copying and drawing tasks on a Microsoft Surface tablet while speaking. The tablet will

INVESTIGATOR STUDY PLAN – REQUIRED

record voice, facial expression, and kinematics of writing/drawing. (<15 min)

- Respiratory function will be assessed by incentive spirometry measuring peak inspiratory volume (<5 min)
- To assess language processing, subjects will perform a self-paced reading task. On a computer screen, subjects will be presented with a word that is part of a sentence. They will read the word and then push a button to advance to the next word. Sentences will vary in syntactical complexity. Comprehension will be assessed by instructing the subject to select the picture correctly illustrating the sentence from multiple choices. We will optimize experimental set-up for PD patients (e.g. large, easy-to-push button). (20 min) If time allows, participants may also complete a guided sentence completion task in which they will be asked to construct a sentence to describe a series of pictures. (5 min)

A sub-group of participants will be invited to participate in an extension study using a smartphone application called Speech Vitals (Aural Analytics). These participants will use the app on their personal smartphone once weekly for 4 weeks (or 4 times total over 8 weeks if they have difficulty with weekly measurements). The app will prompt the user through about 10 minutes of speaking tasks.

- A blood sample will be drawn from peripheral venous stick to send for genetic analysis for PD and dementia-related genes.

Participants will be assigned to either the PD or HC groups depending on their clinical interview / exam.

Estimated total study visit time is 3-4 hours. Participants will be asked frequently if they require a break. If a participant asks to stop the study protocol due to fatigue, they will be allowed to return another day to complete the protocol if they wish. Participants will be compensated for a single study visit, with a \$20 gift card.

All speech recordings will be performed using a head-mounted voice recorder.

Due to the COVID-19 pandemic, we will allow participants to complete the screening visit and portions of the study visit remotely via password-secured Zoom videoconference. These virtual participants must have a device with camera to be able to join a Zoom meeting. They must also have a smartphone to participate in using the Speech vitals app. It has become clinically acceptable to perform many components of neuropsychological evaluation via telehealth. Cognitive tests requiring

INVESTIGATOR STUDY PLAN – REQUIRED

paper forms for the participant to write on will be mailed to participants, with each test enclosed in a separate enveloped marked “do not open until study visit” to avoid practice opportunities. The virtual study participants will only perform the picture description task from the speech protocol. This portion of the virtual visit alone will be recorded for subsequent transcription and analysis. Virtual participants will not perform the majority of the speech protocol, the language laptop task, the dual-tasking drawing/writing task, or the blood draw for genetic markers on the virtual visit day. They will be enrolled in the smartphone sub-study for 4-8 weeks. They will be asked to come in person to UMMS within 6 months to complete the remainder of the study activities. They will not need to repeat cognitive testing done previously, but will need to repeat the speech recording of the picture description. They will receive compensation only at the in person visit. The virtual opportunity will be offered at time of study enrollment, and participants may choose a one-time in person study visit, or a virtual visit followed by in person study visit. The rationale is that not all participants are comfortable with in person contact and this situation remains variable and evolving. Our new structure will allow recruitment to proceed more flexibility, bearing in mind the concerns of our older patient population. If a participant completes the virtual visit but not the in person visit due to any reason, their data will be included but they will not be counted toward the overall enrollment targets and will not receive financial compensation.

There will not be long-term follow-up data collected. The participant will be reminded at study completion that they may be contacted in the future for follow-up or related studies (as indicated in the consent form) unless they contact the study team to decline this option. The PI's contact information will be provided at this time for this purpose. Documentation of those who decline will be kept by the PI to ensure these patients are not contacted.

All relevant assessment tools and questionnaires are attached.

We will be processing blood samples for later analysis at VA Puget Sound Healthcare System. This will include spinning the blood in a centrifuge and aliquoting plasma and buffy coat with a pipette. No analysis will be taking place at UMass, only the centrifuging and aliquoting. Aliquoted samples will be stored in a freezer in the Clinical Research Center.

Aliquoting will take place under a ventilated hood. Waste will be disposed of in the proper biohazard containers. We will be working in the Clinical Research Center under IBC I-631-15.

Smartphone and tablet procedures

Speech Vitals smartphone application (Aural Analytics): Speech Vitals is HIPAA- and GDPR-compliant mobile application and system developed

INVESTIGATOR STUDY PLAN – REQUIRED

by Aural Analytics to collect and analyze speech in clinical studies. It's available for use on iOS and Android devices through the Apple Store and Google Play Store, respectively. The app is downloaded onto the participant's personal phone. Participants sign in using a study-provided user ID and password. The ID and password don't contain any personal information. Technical support questions should be directed to the UMass study team, who will work with Aural Analytics to resolve the issue. A Microsoft Surface tablet will be configured with specialized software for the dual-task procedures. Participants will be asked to perform various speaking tasks while copying shapes and drawing. Voice, facial expression, and manual kinematics will be automatically recorded with time stamp. The UMass study team members will be trained by MIT Lincoln Lab (MIT LL) collaborators in the proper and safe use of audio/video recording.

11) Data and Specimen Banking*

Blood/plasma samples will be taken and shared with VA Puget Sound Health Care System in the bank of [name]. It will be plasma sent and analyzed for LRRK2, GBA and ApoE4 genes. All samples will be de-identified before being sent. They will be stored indefinitely. Blood will be stored in locked freezers on a locked floor in the lab at VA Puget Sound. Only laboratory personnel on the protocol will have access to the samples via possession of a key. For future use of the specimen, [name] research group and local collaborators at the VA Puget Sound Health Care System and University of Washington will be granted access. Specimen may be provided to other collaborators but this will be discussed with [name] first.

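### Objective 3's claim that speech fluctuates with therapy has no described per-session exposure or within-person model, and the Aim 1 sample-size text claims meaningful change from cross-sectional data

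*Combined protocol and SAP*

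**What the plan says.** **Hypothesis.** Section 3, objective 3: "We hypothesize that vocal biomarkers of disease burden will fluctuate based on therapeutic response". The same sentence adds correlation with motor, cognitive and affective severity. Section 4 gives the rationale at the level of the individual: "speech impairment may vary within an individual in response to medications and other therapies". It justifies frequent remote sampling in the same terms: "Since PD symptoms vary both within and between days, and in response to medications".

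**Repeat speech.** Section 10 invites a sub-group of unstated size to use the app "once weekly for 4 weeks (or 4 times total over 8 weeks if they have difficulty with weekly measurements". Virtual participants join this sub-study and later attend in person: "They will not need to repeat cognitive testing done previously, but will need to repeat the speech recording of the picture description".

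**Exposure and state.** After consent, section 10 lists a "medication list (PD and controls, all medications") and an MDS-UPDRS symptom and motor assessment. Section 26 gives session time and device information as examples of app metadata; the list is open-ended.

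**Analysis.** Section 12 covers acoustic classification of cognitive status (Aim 1), linguistic markers by group (Aim 2), and syntax processing by group and sentence type (Aim 3). Section 22 assigns analysis of the app data, including subgroup analyses, to the app vendor without specifying a model.

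**Change.** The Aim 1 sample-size paragraph presents 3-4 MoCA cut points, estimated with 50 PD-MCI, as measuring both severity and clinically meaningful change for later trials. Section 8 describes the "main study: 1 screening session and 1 study visit less than 3 months apart". Section 10 adds: "There will not be long-term follow-up data collected". Section 14 expects cognitive change to take years.

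**The concern.** A fluctuation hypothesis needs three things: repeated outcomes, an exposure that can differ between a person's sessions, and an analysis that compares a person with himself or herself. Only the first is described. A medication list described once per participant can separate people by therapy, but it cannot tell one session from another.

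The order of events matters. Symptom state and time since medication are hard to reconstruct after a recording. Section 26 also restricts collection to pre-specified data, so these items cannot simply be added informally along the way. If they are not captured, the study will hold repeat speech that cannot address the stated hypothesis.

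The Aim 1 wording raises a separate problem. Cut points from a single cross-section grade how impaired people are relative to each other. A later trial that took them as thresholds for meaningful change would be relying on something these data cannot show.

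**Working it through.** **1. The stated figure.** The 50 PD-MCI cannot be reproduced. Section 12 gives no alpha, power, effect size, SD, target AUC or precision. Assuming two-sided 5% and 80% power, 50 v 50 detects (1.960 + 0.842) × √(2/50) = 2.802 × 0.2 = 0.56 SD between groups. That is a difference between people and carries no information about change.

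**2. Requirement against description (fluctuation).**

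| Needed | Described | Where |
|---|---|---|
| Repeat speech | 4 app sessions; repeat picture description (virtual participants) | Section 10 |
| Medication timing or state per app session | None described | Sections 10, 26 |
| State at the study visit | MDS-UPDRS | Section 10 |
| State at each picture description of virtual participants | Unclear | Section 10 |
| Therapy or within-person model | None | Section 12 |
| Contrast created by design | None; there is no intervention | Section 21 |

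**3. Requirement against description (change).** MoCA is given at screening and listed again in the core battery, so two values under 3 months apart may exist. They could inform measurement error. No change score is planned. The CDR and PDAQ could anchor differences between people, but not change, and the plan does not link them to the cut points.

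**4. What the app sessions could show if state were recorded (illustration).** Assumed: two states; a share p of sessions in one of them, independently across sessions; n PD participants; no missed sessions; two-sided 5%, 80% power. From section 10: 4 sessions per person.

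Share of people seen in both states = 1 − p⁴ − (1 − p)⁴:
- p = 0.5: 1 − 0.0625 − 0.0625 = 87.5%
- p = 0.2: 1 − 0.0016 − 0.4096 = 59%
- p = 0.1: 1 − 0.0001 − 0.6561 = 34%

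With k of 4 sessions in one state, a person contributes k(4 − k)/4 to the within-person sum of squares, on average 3p(1 − p). The approximate detectable difference is 2.802/√(n × 3p(1 − p)). For n = 30 and p = 0.5 this is 2.802/√22.5 = 0.59. Averaging noncentral-t power over the random splits, with 3n − 2 degrees of freedom (session number in the model), gives these values in within-person residual SDs:

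| PD participants | p = 0.5 | p = 0.2 | p = 0.1 |
|---|---|---|---|
| 20 | 0.74 | 0.93 | 1.28 |
| 30 | 0.60 | 0.75 | 1.02 |
| 50 | 0.46 | 0.58 | 0.78 |

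If half of the 30 never change state, their row becomes 0.86 / 1.09 / 1.52. Only PD participants count. Section 10 asks both groups about a compatible phone, so 30 users of whom one third are controls (assumed) would mean the 20 row. If state is unrecorded, or varies in nobody, no n suffices.

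**5. Between-person fallback.** With 100 PD and a share a in one therapy group, the detectable difference is 2.802 × √(1/(100a) + 1/(100(1 − a))). For a = 50% / 20% / 10% this is 0.56 / 0.70 / 0.93 between-person SDs, unadjusted and open to confounding by severity.

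**The case against.** The strongest reply is that this is an absence claim about material we cannot see. Section 10 says the assessment tools and questionnaires are attached, section 22 describes the app as customized to the study, and section 26 lists questionnaire responses among the data. A question on medication timing could sit in any of these. That stands, and limits the exposure point to what the visible text describes. It does not reach the missing model, since section 12 would have nothing that uses such an item.

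A reader might infer that symptom state is recorded nowhere. The documents do not support that: the study visit includes the MDS-UPDRS alongside the speech tasks. Section 10 does not list it among the activities virtual participants omit, so whether it accompanies their first or repeat picture description is unclear. The app sessions are where the gap is plainest.

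A reader might also infer that removing the fluctuation wording would put objective 3 in order. It would not. Section 12 describes no analysis relating vocal biomarkers to motor or affective scores either; its three aims follow the primary outcomes in section 9, not the objectives in section 3.

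On Aim 1, the mention of future trials can be read as intended later use. That softens the sentence, but it still says the sample suffices for a measure of change.

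**Conclusion.** Both points hold at low severity. In the visible text, 4 app sessions per person are planned and none is described with medication timing or symptom state, and section 12 has no therapy or within-person model. Separately, the Aim 1 text attaches clinically meaningful change to cut points from a cross-sectional design with no planned cognitive follow-up visit, change analysis or anchor; only severity is supported.

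A reader might go further and conclude that objective 3 is untestable or that a main result is at risk. Neither follows. The severity scales and medication list are collected, so cross-sectional associations remain possible once an analysis is stated. Objective 3 is not among the primary outcomes in section 9, and section 25 calls the study exploratory.

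The conclusion rests on the visible text and on the forms and app prompts not already capturing state. It does not rest on the power figures, whose sub-study size, state shares and independence across sessions are all assumed.

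**What to change.** **Fluctuation.** For PD participants, record time since last PD medication and self-rated current state at each app session and at the repeat picture description, leaving usual treatment unchanged. State the sub-study size, split by PD and control. Add to section 12 an exploratory, observational mixed model of the app sessions in PD participants: random intercept, session number, person mean, and within-person deviation in state or time since medication. Report how many participants contribute more than one state, because only they inform the contrast. Time since medication is a proxy for therapeutic response and should be described as one.

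If the forms or app already capture these items, say so in section 10 and add only the model. If the items are not added, restrict objective 3 to cross-sectional association and state that analysis in section 12, including the motor and affective scores.

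**Aim 1.** Delete the reference to clinically meaningful change, so that the cut points are described as a measure of severity only.

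**Cost.** A short amendment, two brief questions added to sessions of about 10 minutes, some app vendor work or a study-team log, and one extra model. The result may be inconclusive if few participants change state. The wording-only route needs the amendment and a stated cross-sectional analysis.

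### Does Aim 2 need a written rule on whether the remote or the in-person picture description is analysed?

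*Combined protocol and SAP*

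**What the plan says.** Section 10 describes the pathway added because of COVID-19. At the remote visit, "The virtual study participants will only perform the picture description task from the speech protocol". On the use of that recording it says: "This portion of the virtual visit alone will be recorded for subsequent transcription and analysis". Attendance then follows: "They will be asked to come in person to UMMS within 6 months". At that visit, "They will not need to repeat cognitive testing done previously, but will need to repeat the speech recording of the picture description". The choice is the participant's: "participants may choose a one-time in person study visit, or a virtual visit followed by in person study visit". One reason is given: "The rationale is that not all participants are comfortable with in person contact". For those who never attend in person, "their data will be included but they will not be counted toward the overall enrollment targets".

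Just before this, section 10 says without exception that speech is recorded with a head-mounted device. Its list of speech tasks includes "sustained phonation of vowel sounds, reading nonsense words, reading sentences and passages, description of a picture of a scene".

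Section 12, Aim 2, takes as primary outcome the rate of pauses preceding verbs, per 100 verbs. The secondary outcomes are pause duration, pauses before nouns, speaking rate and the share of well-formed sentences. A mixed model with three-level group is the primary analysis; ANOVA and pairwise t-tests are also named. Section 12 names no source task, no choice between two recordings and no mode term.

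**The concern.** Three data patterns can arise: in person only, remote then in person, and remote only. Pathway is self-selected, so recording mode is not balanced across PD-MCI, PD with normal cognition and controls by design. A videoconference channel could plausibly alter detected pauses and timing, which most of the Aim 2 outcomes measure. If remote recordings were pooled with head-mounted ones, and remote use or the size of the channel effect differed by group, part of any group difference would come from the recording method. Treating two recordings of one person as independent would be a separate error. Section 12 rules out neither.

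Aim 1 is touched only if its acoustic models use the picture description, because the other speech tasks are not done at the remote visit.

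**Working it through.** **1. Is there a plan figure to reproduce?** No. Aim 2 states no alpha, power, SD or effect size. Groups of 50 come from section 4 (Background). The 5% level, channel shifts and uptake below are assumptions.

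**2. Which recording does the text point to?** Three statements in section 10, side by side:
- speech is recorded with a head-mounted device;
- cognitive tests done remotely are not repeated;
- the picture description done remotely is repeated.

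Repeating this one task has little purpose unless the in-person file is the study recording. For anyone who attends in person, the sensible reading is one in-person recording each. What stays open is remote-only speech.

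**3. Effect of adding remote-only speech.** Suppose a extra people in one group and b in the other, each shifted by d SD, with no true difference:

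false difference = d × [a/(50+a) − b/(50+b)]

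| Added | Difference in remote share | False difference, d = 0.5 / 1 | Rejection, d = 0.5 / 1 |
|---|---|---|---|
| 5 v 2 | 5/55 − 2/52 = 0.052 | 0.026 / 0.052 SD | 5.0% / 5.1% |
| 10 v 2 | 10/60 − 2/52 = 0.128 | 0.064 / 0.128 SD | 6.0% / 8.7% |

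Rejection rates come from 100,000 simulated trials per row and shift, with a two-sided t-test at 5%. For 10 v 2 the standard error is √(1/60 + 1/52) = 0.189 SD, so the false difference is about one third (d = 0.5) or two thirds (d = 1) of a standard error.

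With a count-type pause rate and remote recording raising it 1.5-fold (also assumed), 5 v 2 gives 5% and 10 v 2 gives 6–7%.

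**4. If the t-test counts only after a significant ANOVA.** This is one reading of the plan's sequence. With three groups and the third also at the lower remote share, pairwise rejection is 2.6% with no remote speech. It is 2.5% / 2.5% for 5 v 2 and 3.2% / 5.0% for 10 v 2.

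**5. Would a mode term settle it?** Only if the shift is the same in every group. With shifts of 1 v 0.5 SD and 10 remote-only added to each group, the false difference is (10/60) × 0.5 = 0.083 SD. Rejection is 6.3% without the term and 7.2% with it.

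**6. What does an in-person-primary rule cost?** People who came by the remote route supply a second-exposure recording. With 40% v 10% on that route and a shift of 0.5 SD, the false difference is 0.30 × 0.5 = 0.15 SD whether the shift comes from the channel (remote file used) or from repetition (in-person file used). Simulated rejection is 11.25% and 11.2%. Restricting to first-exposure in-person recordings avoids both but loses precision: the difference detectable at 80% power rises from 0.57 SD (50 v 50) to 0.62 (40 v 45) or 0.67 (30 v 45).

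**The case for a change.** The strongest case for a change is that the in-person reading is implied, not stated, and cannot cover remote-only participants, whose data section 10 expressly includes. Aim 2 names a primary outcome and a primary analysis, so the choice of recording should not wait until data are seen. If remote files replaced in-person ones, with 40% v 10% remote use, rejection would be 11% at 0.5 SD and 28% at 1 SD. If both files per person were treated as independent, it would run from 7.0% (20% recorded twice, within-person correlation 0.5) to 14.4% (all recorded twice, 0.8). A few sentences would close the gap without touching the planned 100 patients and 50 controls.

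The omission stands, as does the mismatch between the unqualified head-mounted statement and the videoconference recording. The larger figures do not carry over. Replacing in-person files runs against the reason for the repeat, and the uptake gap is not in the documents: the one stated motive is comfort with in-person contact, not cognitive status. Counting one person twice as independent is an error no competent analyst would make, and nothing in the plan calls for it.

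The tie to the picture description is also inferred. The share of well-formed sentences needs self-generated speech, but the task list is open-ended and section 10 has an optional sentence-construction task that would supply some.

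**Conclusion.** No change to the plan follows. Section 12 leaves a detail unwritten that section 10 largely answers, and analysts would fill it by using the in-person recording. The open remainder is remote-only speech from people outside the enrolment target. Its effect on a nominal 5% test is 5.0–6.0% at an assumed 0.5 SD shift. It reaches at most 8.7% among the common-shift cases at 1 SD, and that takes ten such people in one group of 50 against two in another. With equal uptake and a common shift there is no bias, only some loss of precision.

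These sizes rest on assumed shifts and uptake; the documents support neither, so no bias can be derived from them. Further rules on mode would be added sensitivity analyses, or a trade of channel bias for second-exposure bias that is equally large for an equal shift. The possible gap of up to 6 months between cognitive testing and the in-person recording matters little on the plan's own view in section 14 that cognition in PD changes over years. For a study that section 25 describes as exploratory, this is a point of wording.
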